## Abstract

**Background:** Antidepressants are commonly prescribed by primary care providers for treating depression, anxiety, and other conditions. A trial and error approach is typically used to identify effective therapy. Treatment efficacy and safety of many antidepressants can vary based on the presence of certain diseases and metabolism gene types. Pharmacogenomic (PGx) testing provides phenotypic classification of individuals as poor, intermediate, extensive, and ultra-rapid CYP450 metabolizers. This allows more accurate drug selection for efficacy and dosing to minimize toxicity.

**Objective:** To determine the preliminary effectiveness of PGx testing for selection of effective antidepressant, medication adherence, depressive symptoms, and healthcare utilization. To determine acceptability of PGx testing in primary care among patients and providers.

**Methods:** This is a 6-month randomized, wait-listed, controlled pilot trial conducted in 6 department of family medicine (DFM) clinics at the University of Michigan (UM). We will enroll physicians practicing at a UM DFM clinical site who are willing to utilize PGx test results in conjunction with treating patients prescribed certain antidepressants. We will also enroll patients of these DFM physicians who are adults with a new prescription for an antidepressant (within the past 4 weeks) including patients who have switched to a new antidepressant from another antidepressant or have added on a new antidepressant to current antidepressant therapy. Patients are excluded if taking an antidepressant for more than 4 weeks and if they have had PGx testing in the past.

Physician participants will complete a baseline survey to assess demographics, and knowledge, acceptability and utility of PGx testing for this population. At the conclusion of the study, physician participants will complete a semi-structured interview to assess knowledge, satisfaction, feasibility, acceptability, effectiveness, barriers to widespread adoption, and utility of PGx testing.

All patients will complete a baseline, 3-, and 6-month assessment; control patients will have an additional 9-month assessment. Data to be collected include reasons for antidepressant use, depression and anxiety symptoms and severity, functional health status (SF-12), PGx knowledge, work status changes, demographic information, physician and emergency department visits, adverse effects, and medication alterations and adherence.

## 2.0 Introduction

According to the Centers for Disease Control and Prevention, between 2011 and 2014, 10.7% of Americans reported taking at least one antidepressant in the past month. [1] Antidepressants were the third most commonly used medication after cholesterol and pain medications.

Antidepressants are prescribed for the management of depression, anxiety, and other conditions. Given that the time from initiation of pharmacologic treatment to clinical effect takes two to four weeks,[2, 3] coupled with the fact that the initial medication may not be effective, thus necessitating adjustments to dosages or medications, treatment with an antidepressant can be a long and complicated process, during which patients still experience symptoms.

Strategies to improve treatment often include switching patients to a different antidepressant or prescribing an additional antidepressant.[4]

One reason for poor response to antidepressants can be attributed to the drug metabolism process. Many of the most commonly prescribed antidepressants undergo phase one xenobiotic metabolism by a class of enzymes in the P450 superfamily. This family of enzymes exhibits a high degree of genetic polymorphism, resulting in variable metabolism. Because of this variation in P450, we can classify individuals as poor, intermediate, extensive, and ultra-rapid metabolizers. The consequence of this population heterogeneity is that medications are metabolized at different rates and plasma concentrations of specific drugs can be outside of the optimal range, which may result in adverse drug events or lack of therapeutic effect. Because of these two medication outcomes, treatment may be discontinued.

Pharmacogenomic (PGx) testing of several cytochrome P450 genes and the most frequently described functional variants (CYP2D6, CYP2C9, CYP2C19, and CYP1A2) can be used to predict the metabolic capacity of an individual. For example, it is estimated that 5-10% of Caucasian individuals are poor metabolizers and 1-2% are ultra-rapid metabolizers based on CYP2D6 phenotypes.[5] By knowing a patient's genetic information and the drug's major metabolic pathway, we can prospectively assess the appropriateness of specific medications, modifying the dosing or using enhanced monitoring. By identifying the approximately 10% of individuals who will not metabolize antidepressants properly via the CYP2D6 pathway, we may be better able to identify effective treatment options and minimize adverse effects.

While the promise of this personalized medicine approach has been high, clinical uptake of PGx testing has lagged behind due to a combination of factors, including but not limited to provider confusion, lack of expertise, lack of studies confirming clinical utility, cost of testing, and a lack of an integrated approach.[6]

## 3.0 Objectives

PGx testing could greatly improve the use of antidepressants by aiding prescribers in identifying proper medications for individual patients; thus potentially improving medication adherence, as well as reducing symptoms and antidepressant side effects.

This pilot study will explore the use of PGx testing in primary care, and is guided by several specific aims:

Specific Aim 1: To determine the effect of PGx testing on the primary outcome of physician treatment decisions, as measured by the change in the proportion of patients who are prescribed medications at baseline that are contraindicated according to the PGx test, compared to the proportion at six-month follow-up.

Specific Aim 2: To determine the effect of PGx testing on secondary outcomes measures of interest, including change in symptoms and severity and medication adherence from baseline to six-month follow-up.

Specific Aim 3: To determine the acceptability of PGx testing in primary care among patients and physicians.

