## 5.0 Study Procedures

### 5.1 Study Design

This study will include two different populations of participants; primary care physicians and their patients who have been recently prescribed and taking one of the following antidepressants: citalopram (Celexa), escitalopram (Lexapro), fluoxetine (Prozac, Prozac Weekly, Rapiflux, Sarafem, Selfemra), fluvoxamine (Luvox, Luvox CR), paroxetine (Paxil, Paxil CR), sertraline (Zoloft), duloxetine (Cymbalta, Irenka), venlafaxine (Effexor, Effexor XR), nortriptyline (Aventyl, Pamelor), bupropion (Forfivo, XL, Wellbutrin, Wellbutrin SR, Wellbutrin XL), mirtazapine (Remeron, Remeron Soltab), or vortioxetine (Trintellix). We will recruit and enroll approximately 30 UM DFM physicians to participate in this study. For physician participants, we will obtain consent and then conduct assessments of baseline PGx knowledge, as well as semi-structured interviews and surveys regarding their experiences at the conclusion of the study. Please see Figure 1 for physician participant study flow.

From those participating physicians, we will recruit 100 of their adult patients who have been newly prescribed one of the antidepressants listed above. These patient participants will be enrolled in a six-month randomized wait-listed control pilot study.

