Patient participants will meet with study staff for consent and baseline data collection at a Michigan Clinical Research Unit (MCRU) in either Domino's Farms or the Cardiovascular Center. Once consent and baseline data collection are complete, participants will have their blood drawn by MCRU laboratory staff. A single 4 mL Lavender top EDTA tube of blood will be drawn. Once the blood draw is complete, study staff will send the sample to Progenity for analysis. After the baseline assessment is complete, patient participants will be randomized equally to either have their test results sent immediately to their participating primary care physicians once available, or to have their test results sent in three months. Randomization will be stratified by physician in ten block units to ensure balance by physician. PharmDs on the research team ([name] and [name]) will be available to consult with physician participants at any time during the study; however, our study PharmDs will meet with each participating physician at least once, when their first patient PGx test results are available to provide general, as well as patient specific education about the PGx test and results. These consultations will help physicians to interpret PGx test results, and may help to guide treatment decisions, if necessary. Study pharmacists or staff will not

provide PGx results to patients; it is up to the patient's physician to provide this information if he/she feels it is appropriate. Likewise, although study pharmacists may make treatment recommendations based on the PGx test results, it is up to the treating physician to decide whether to act on those recommendations. All intervention patient participants will be followed for a total of 6 months, with phone-based follow-up assessments occurring at 3- and 6-months. All control patients will be followed for 9 months, with phone-based follow-up assessments occurring at 3-, 6-, and 9-months. Please see Figure 2 for patient participant study flow.

Figure 1. Physician Participant Study Flow

[figure not shown]
[figure not shown]

Figure 2: Patient Participant Study Flow

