Physicians and patients enrolled in this study will be exposed to minimal risk. Participants in both arms of the study will undergo PGx testing. Physicians for intervention group participants will receive PGx test results as soon as they are available, whereas those participants in the waitlisted control group will receive their test results three months after enrollment. Because the current standard of care does not involve the use of PGx testing, our waitlisted control group is not exposed to any additional risk above and beyond usual care. To clarify, the intervention under investigation in this study is the PGx test. We will not directly intervene in the clinical care of a patient, as all clinical decision making is at the discretion of the physician managing a patient's care. All participants in this study may benefit because their antidepressant medication may be tailored to their pharmacogenomic profile. Although both populations of participants run risks associated with breaches of privacy due to electronic storage of study data, every effort will be made to minimize these risks.

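### Aim 1 judges the effect of PGx testing at six months, three months after control results are released; the month-3 comparison, the only one with an unreleased control, is not named primary

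*Combined protocol and SAP*

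**What the plan says.** - Section 3.0, Aim 1: the primary outcome is physician treatment decisions. It is measured as the proportion of patients whose baseline medication is "contraindicated according to the PGx test, compared to the proportion at six-month follow-up". No between-arm contrast is written into the aim. Aim 2 (symptoms, severity, adherence) uses the same six-month window.
- Section 5.1 defines what is being tested: "the intervention under investigation in this study is the PGx test". It describes the control condition as usual care: "Because the current standard of care does not involve the use of PGx testing".
- Section 5.1, release: intervention physicians get results as soon as they are available, "whereas those participants in the waitlisted control group will receive their test results three months after enrollment".
- Section 5.1, follow-up: months 3 and 6 for the intervention arm; months 3, 6 and 9 for controls.
- Section 5.5.2 and Table 2: medications and medication changes are recorded at every assessment, including month 3. Treatment is also extracted from MiChart.
- Section 5.6: t-tests compare the arms at each time point and at matched times since release (intervention baseline against control month 3). Mixed models with a time-by-group term are fitted on both clocks. No time point or contrast is named primary.

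**The concern.** By section 5.1's own definitions, the question is PGx results against no PGx results. The time point tied to the primary outcome falls after both arms have been released, so Aim 1 fails on either reading.

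- **Before-after change.** There is no comparator without results. Section 2.0 describes switching or adding antidepressants as common practice, so a fall in the contraindicated share could be ordinary prescribing.
- **Between-arm difference at six months.** This estimates early against delayed release. It shrinks as controls catch up. A result near zero could not be told apart from a test that works and that both arms have acted on.

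The month-3 comparison is planned but has no special status. Choosing it once results are known would be a post hoc selection.

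**Working it through.** **Schedule.** Time with released results, in months:

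| Assessment | Intervention | Control | Arm contrast |
|---|---|---|---|
| 3 | up to 3, less laboratory turnaround | 0 | results vs none |
| 6 | up to 6, less turnaround | about 3 | early vs delayed release |
| 9 | not assessed | about 6 | none |

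Section 5.6 implies that the control month-3 call precedes release, because it pairs that call with the intervention baseline. The order is not stated outright.

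The plan gives no effect size, alpha, power or contraindicated share, so there is no figure to reproduce. Everything below is illustration and ignores clustering.

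**Dilution.** Let s be the contraindicated share before release, corrected at constant rate k after release, with k = ln 2 / half-time.

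- Month-3 difference: s(1 − e^(−3k))
- Month-6 difference: s(e^(−3k) − e^(−6k))
- Ratio of month 6 to month 3: e^(−3k)

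For s = 20%:

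| Half-time (months) | Month 3 (points) | Month 6 (points) | Kept at month 6 |
|---|---|---|---|
| 0.5 | 19.7 | 0.3 | 1.6% |
| 1.5 | 15.0 | 3.75 | 25% |
| 3 | 10.0 | 5.0 | 50% |
| 6 | 5.9 | 4.1 | 71% |

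**Power.** Per arm n = 100 × 0.80 / 2 = 40 (section 5.6). Assumptions: 75% corrected within three months of release, two-sided 5% pooled z-test, exact binomial power.

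| Contrast | s = 10% | s = 20% | s = 30% |
|---|---|---|---|
| Month 3: s vs 0.25s | 0.295 | 0.574 | 0.770 |
| Month 6, correction continues: 0.25s vs 0.0625s | 0.014 | 0.088 | 0.194 |
| Month 6, correction complete: 0.25s vs 0.25s | 0.013 | 0.043 | 0.057 |
| Month 3, 50 per arm (MiChart complete) | 0.325 | 0.664 | 0.861 |
| Month 3, 30% ordinary switching in controls: 0.7s vs 0.25s | 0.135 | 0.304 | 0.429 |
| Same switching in both arms: 0.7s vs 0.175s | 0.173 | 0.425 | 0.596 |

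**Contamination at month 3.** Patients are randomised within physician: "Randomization will be stratified by physician in ten block units to ensure balance by physician". Education starts early: "our study PharmDs will meet with each participating physician at least once, when their first patient PGx test results are available". With 100 patients and about 30 physicians (about 3.3 each) and blocks of ten split 5:5, a physician with m patients has both arms with probability 1 − 2·C(5,m)/C(10,m). That is 83% for m = 3 and 95% for m = 4.

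Suppose controls receive a fraction c of the 75% correction before release. At s = 20% the month-3 difference is 20(1 − 0.75c) − 5:

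- c = 0.2: 12.0 points, power 0.440; month 6 gives 3.0 points
- c = 0.4: 9.0 points, power 0.304; month 6 gives 2.25 points

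Contamination weakens month 3, but month 6 stays worse.

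**Time coding in the mixed model.** Section 5.6 does not say how time enters. Suppose it is linear, data are complete and control month 9 is included. With intervention values 20, 5, 1.25 and control values 20, 20, 5, 1.25, a true month-3 difference of −15.0 points is fitted as −6.4 (interaction −0.75 per month). With complete correction (20, 5, 5 and 20, 20, 5, 5) it is fitted as −5.5 (interaction −0.50 per month).

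**The case against.** The strongest reply is that the plan already produces the right contrast. Medications are recorded at month 3, MiChart documents changes, and section 5.6 compares the arms at every time point. Control months 0 to 3 also give a concurrent period without results, from which background drift can be estimated. This stands: no data are lost and the outcome itself is sound. But the plan ties its primary aim to a different time point, and nothing raises the month-3 comparison above the others.

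Six months may have been meant on the time-since-release clock, since controls are followed to month 9. Section 3.0 does not say so. On that clock both arms have released results, and recent starters are set against controls three months further into treatment. That is not a same-time randomised contrast.

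This is a pilot seeking preliminary effectiveness, with no stated power target. That lowers what can be asked of precision, but not the need to estimate the intended contrast.

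The illustrations depend on assumed rates. With a six-month half-time, month 3 gains little: 5.9 against 4.1 points, or 4.1 against 2.9 with a one-month turnaround. Fisher's exact test at 40 per arm lowers month-3 power to about 9%, 41% and 68% for shares of 10%, 20% and 30%. Both points stand. Under the constant-rate model, month 3 is nevertheless never the worse choice.

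**Conclusion.** The concern holds and must be fixed for Aim 1. The contrast named for the primary outcome has no comparator without results, on either reading, so followed as written it does not isolate the effect of PGx testing. This conclusion rests on the release and assessment schedule alone.

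The size rests on assumptions. Over correction half-times of 0.5 to 6 months, the six-month arm difference keeps between 1.6% and 71% of the month-3 difference. Month 3 is not a well-powered test either, and within-physician contamination and ordinary switching would weaken it further. It should be reported as a pilot estimate.

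For Aim 2 the six-month choice is partly a trade-off, because symptoms and adherence may respond later. The must-fix rating does not extend to it.

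**What to change.** 1. **Aim 1.** Name as primary the between-arm difference at three months in the proportion on a PGx-contraindicated prescription. Take the prescription from MiChart on the same study day in both arms, the day before the scheduled control release. Report it with a confidence interval as a pilot estimate.
2. **Aim 2.** Report month-3 differences as the PGx-versus-no-PGx contrast. Keep six months, labelled early versus delayed release.
3. **Models.** Code time as categorical in the time-in-study model, so that the month-3 group-by-time term is estimated directly. Label the time-since-release model descriptive.
4. **Sequence.** State that the control month-3 call is completed before results are sent, and flag later calls. This matters mainly for the call-based Aim 2 measures.
5. **Contamination.** Report how many control patients had a physician who, before their month 3, had already received another patient's results or the pharmacist session.

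**Cost.** Protocol and SAP wording, a sequencing rule and a dated MiChart extraction; no new visit or measure. The downside is that month 3 allows at most three months of exposure, less laboratory turnaround, so later effects show only at six months. As an illustration, at a 20% share and k = ln 4 / 3, a one-month turnaround makes the comparison 20% against 20% × e^(−2k) = 7.9%. Power then falls from 57% to 36%.

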### **5.4.2 Patient Participants**

To be included in this pilot trial, participants must:

- Be a patient of a participating physician
- Have a new prescription for a certain antidepressant recorded in MiChart (within the previous 4 weeks prior to screening)
- Be currently taking the new antidepressant
- Be willing to undergo PGx testing via single tube blood draw
- Be at least 18 years old

Participants will be excluded from this pilot trial if they:

- Do not speak English
- Have previously undergone PGx testing
- Are unable to provide their own consent to participate in the study
- Have been taking the new targeted antidepressant for longer than 4 weeks (prior to screening)

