### **5.5.2 Patient Participants**

Patient participants will be screened for inclusion/exclusion criteria prior to consent and enrollment. After enrollment, all patient participants will complete a baseline, 3-, and 6-month assessment. Control patients will have an additional 9-month assessment of the previously mentioned items. All baseline data will be collected via paper forms and then transferred into REDCap, whereas 3-, 6-, and 9-month assessments will be conducted via phone and entered directly into REDCap by study personnel. The constructs, measures, and data collection times are shown in Table 2. In addition to these measures collected during data collection visits, data will be extracted from MiChart to document treatment, including medication changes, and healthcare utilization for patient participants during the study. We will also extract any available PHQ-9 and GAD-7 data, which is now collected as a part of routine clinical practice. Surveys/interviews will be audio recorded when permitted by participants.

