**Table 2. Patient Participant Measures**

Construct	Measure	Assessment Time			
		Baseline (via paper survey)	3 months (via phone)	6 months (via phone)	9 months (Control Only; via phone)
Reason antidepressant was prescribed		X	X	X	X
Depression Symptoms and Severity	Personal Health Questionnaire Depression Scale (PHQ-8)	X	X	X	X
Anxiety Symptoms and Severity	Generalized Anxiety Disorder 7-Item Scale (GAD-7)	X	X	X	X
Functional Health Status	12-Item Short Form Survey (SF-12)	X	X	X	X
PGx Knowledge	Investigator Developed	X			X
Missed days of work	Work Productivity and Activity Impairment Questionnaire (WPAI)	X	X	X	X
Demographic information		X			
Health history	Smoking history, BMI	X			
Healthcare utilization	Physician visits, hospital and ER admissions	X	X	X	X
Adverse Drug Reactions	Antidepressant Side- Effect Checklist (ASEC)	X	X	X	X
Medication and medication changes	Medications prescribed and number of medication changes	X	X	X	X
Medication Adherence	Adherence to Refills and Medication Scale (ARMS)	X	X	X	X
	Pill count	X	X	X	X
	Three-Item Self-rated Adherence Scale	X	X	X	X

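### Aim 2 measures change in adherence from an early baseline in patients selected as current takers, so within-arm change is likely to lean towards decline and the time-since-release comparisons of adherence are biased

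*Combined protocol and SAP*

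**What the plan says.** Section 3.0, Specific Aim 2, names the outcome as "change in symptoms and severity and medication adherence from baseline to six-month follow-up".

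Section 5.4.2 sets who is measured at baseline. Patients must "Have a new prescription for a certain antidepressant recorded in MiChart (within the previous 4 weeks prior to screening") and must "Be currently taking the new antidepressant". They are excluded if they "Have been taking the new targeted antidepressant for longer than 4 weeks (prior to screening"). Both 4-week limits run to screening, and section 5.5.2 puts screening before the baseline visit: "Patient participants will be screened for inclusion/exclusion criteria prior to consent and enrollment". No maximum gap between the two is given. The Abstract also admits "patients who have switched to a new antidepressant from another antidepressant or have added on a new antidepressant to current antidepressant therapy", so the prescription is new but not always the patient's first antidepressant.

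Table 2 lists three adherence measures, all taken at baseline and at every follow-up: the "Adherence to Refills and Medication Scale (ARMS"), a pill count, and the "Three-Item Self-rated Adherence Scale". I found no rule for scoring refill items when no refill has yet come due, and none for counting a drug that has been stopped or switched.

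Section 5.1 randomises equally after baseline. Results go to the physician as soon as available in one arm and at three months in the other. Section 5.6 plans between-arm t-tests at each time point, and mixed models for change with a time-by-group interaction. It runs the models on two time scales: time in study, and time since results were released. The second sets months 0 to 6 of the intervention arm against months 3 to 9 of the control arm. A matching t-test compares the intervention arm at baseline with the control arm at month 3.

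**The concern.** A change score is informative only if the quantity can vary in the same way at both ends. Here it cannot. Entry requires current use, so nobody at baseline has stopped the new drug, whereas at 3 and 6 months some may have. On the scale with refill content, a patient who habitually refills late has no late refill of the new drug to report until one falls due, but can report it later. On both counts the change from baseline can move more easily towards worse adherence than towards better.

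Two results are at stake. The first is the within-arm trend, which section 5.6 says the mixed models will assess. A decline there could be read as testing failing to help, or could hide a real gain. The second is the time-since-release comparison. Its control origin is month 3, when stopping is possible and refills have normally come due, while its intervention origin is the early baseline. The artefact then enters one arm only and makes that arm look worse.

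**Working it through.** The documents give no effect size, standard deviation or power calculation for adherence, so there is no planned figure to reproduce. The check has four steps.

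**1. Share of patients with no refill yet due at baseline.** Time from prescription to screening is at most 28 days (section 5.4.2) and is taken here as uniform on 0 to 28. The gap g from screening to baseline and the days' supply are not in the documents. Both are assumed, with the gap uniform on 0 to g.

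For a 30-day supply and g of 7, 14 or 28, the share is 1 − (28 + g − 30)² / (2 × 28 × g):

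- g = 7: 1 − 25/392 = 0.94
- g = 14: 1 − 144/784 = 0.82
- g = 28: 1 − 676/1568 = 0.57
- g = 42 (a different region of integration): (30 × 28 − 28²/2) / (28 × 42) = 448/1176 = 0.38
- baseline on the screening day: 1.00

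For a 60-day supply the share is 0.96 at g = 42 and 1.00 for the shorter gaps. For a 90-day supply it is 1.00 throughout. The range is therefore about 38% to 100%, and the documents do not place the trial within it.

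**2. Does constant behaviour score as a decline on every measure?** No. Pill count was simulated with a constant daily probability of taking a dose (assumed Beta(6, 2)). The mean ratio was 0.750 at baseline and 0.750 at follow-up. Keeping only patients with at least one dose in the past 7 days gave 0.751 and 0.751. The artefact is confined to refill content that cannot yet register and to the exclusion of stoppers at entry.

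**3. Where it cancels.** Let b be the amount, in SD units, by which baseline understates lapses.

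- Within each arm, the apparent decline is b.
- Between arms on time in study, both start from the same kind of baseline: b − b = 0.
- Between arms at the same follow-up visit, baseline is not used: 0.
- Between arms on time since release, only the intervention arm starts from the early baseline: b − 0 = b, against the intervention arm. The t-test of intervention baseline against control month 3 is also distorted, because the two visits differ in what can register.

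**4. What b would do, if its size were known.** Section 5.6 expects 100 patients and 80% retention: 100 × 0.80 = 80, about 40 per arm. With an assumed SD of change of 1 and a two-sided 5% normal test, the between-arm standard error is √(2/40) = 0.224. The false-positive rate is Φ(b/0.224 − 1.96) + Φ(−b/0.224 − 1.96):

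| b (assumed) | false-positive rate, time since release |
|---|---|
| 0 | 5% |
| 0.1 | 7% |
| 0.2 | 15% |
| 0.3 | 27% |
| 0.5 | 61% |

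These rows show sensitivity to an assumption. They do not estimate what this trial would show.

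**The case against.** The strongest reply is that Aim 2 asks for the effect of testing, which is a between-arm question, and that section 5.6 already compares randomised arms at each visit and through an interaction. Any shared ceiling cancels there. That stands. A reader might infer that the main randomised comparison of adherence is biased; the documents do not support it. The reply does not reach the within-arm trend, which section 5.6 also assesses, or the time-since-release analyses, where nothing cancels. Nor does the month-6 comparison rescue Aim 2 as worded, because by then both arms have had results released.

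Second, a reader might infer that unchanged behaviour scores as a decline on adherence generally. It does not. Only one of the three measures shows refill content, and only by its name; the documents give neither its items nor its recall period. Pill count is flat under constant dose-taking. Current use does not mean no missed doses, so dose-taking can vary at baseline. Stopping later is a real change in behaviour, and the Introduction treats discontinuation as a consequence of poor drug fit. The narrower point remains: on persistence, a baseline made up entirely of users can move only one way.

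Third, it is tempting to say that nearly everyone is measured before any refill. That depends on days' supply and on the delay to baseline, neither of which is stated. Section 5.2.2 includes recruitment by batched letters followed by phone calls, which could lengthen the delay. Switch and add-on patients may also answer for older drugs. This objection stands against any single figure.

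**Conclusion.** The concern holds in a limited form. Within-arm change in adherence from baseline is hard to interpret and is likely to lean towards decline whatever the effect of testing. The time-since-release model and the matching t-test carry the same distortion into a between-arm result, against the intervention arm. Same-visit and time-in-study comparisons between arms are not biased by it.

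The direction follows from the entry criteria and from the refill content implied by the scale's name. The size does not follow from the documents, because it needs the days' supply, the screening-to-baseline gap and the scale's scoring. A reader who wanted a firm probability of a false decline would have to supply b, and the documents offer no basis for choosing it, including for ruling out a value near zero. The refill and selection argument applies to adherence and does not carry over to the symptom part of Aim 2. As this is a secondary outcome of a pilot, the priority is minor.

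**What to change.** In section 3.0, define the Aim 2 adherence outcome as the between-arm difference in adherence level at follow-up. Make 3 months the main comparison, since it is the only follow-up before control results are released. Report 6 months as early versus delayed release, not as tested versus untested.

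In section 5.6, use baseline adherence at most as a covariate and not as a response. Leave adherence out of the time-since-release model and out of the t-test of intervention baseline against control month 3. Say that within-arm change in adherence from baseline will not be read as an effect of testing. Starting the change at month 3 is not a substitute test of effect, because by then the intervention arm has no value from before its results were released.

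It would also help to state how refill items are scored when no refill has come due, and how a stopped or switched drug is counted.

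The cost is a few sentences, with no new data or visits. What is given up, for adherence only, is the baseline-to-six-month change statement and the re-aligned analysis.
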